# Statistical Analysis Plan

Taisho Pharmaceutical R&D Inc.  
Protocol TS121-US201

Statistical Analysis Plan (SAP)

Final 2.0  
18 Dec 2018  
CONFIDENTIAL

# Statistical Analysis Plan

Taisho Pharmaceutical R&D Inc.  
Protocol TS121-US201

Final 2.0  
18 Dec 2018  
CONFIDENTIAL

Statistical Analysis Plan (SAP)

## Table 2 Tables to be Included in Section 14 of the Clinical Study Report

*Note: Top line tables are indicated \**

---

SECTION 14.1:	Demographic Data
*Table 14.1.1.1	Patient Disposition by Treatment Group and Overall (All Randomized Patients)
Table 14.1.1.2	Patient Disposition by Treatment Group and Overall (Safety Analysis Population)
Table 14.1.1.3	Patient Disposition Through End of Placebo Lead-in (All Consented Patients)
Table 14.1.2.1	Demographics and Baseline Characteristics including Screening Height, Weight and Body Mass Index (Safety Analysis Population)
*Table 14.1.2.2	Hamilton Depression Scale HAM-D Total Score at Screening and Baseline (Safety Analysis Population)
*Table 14.1.3	Baseline Major Depressive Disorder Characteristics (Safety Analysis Population)
Table 14.1.4	Medical History and Psychiatric History (Safety Analysis Population)
Table 14.1.5	Concomitant Medications (Safety Analysis Population)
SECTION 14.2:	Treatment Compliance, PK, Efficacy and PD Data
Table 14.2.1	Treatment Dose Compliance (Safety Analysis Population)
*Table 14.2.2.1	Montgomery-Asberg Depression Rating Scale (MADRS) Total Score Observed and Change from Baseline by Treatment and Visit (Intent to Treat Population)
Table 14.2.2.2	Montgomery-Asberg Depression Rating Scale (MADRS) Item Response Frequency by Treatment and Visit (Intent to Treat Population)
*Table 14.2.2.3	Analysis of Montgomery-Asberg Depression Rating Scale (MADRS) Total Score Change from Baseline Least Squares Treatment Mean Differences by Visit (Intent to Treat Population)
Table 14.2.2.3.1	Multiple Imputation Method for Missing Visits Analysis of Montgomery-Asberg Depression Rating Scale (MADRS) Total Score Change from Baseline Least Squares Treatment Mean Differences by Visit (Intent to Treat Population)
*Table 14.2.2.4	Analysis of Montgomery-Asberg Depression Rating Scale (MADRS) Total Score Change from Baseline Model Summary (Intent to Treat Population)
Table 14.2.2.4.1	Multiple Imputation Method for Missing Visits Analysis of Montgomery-Asberg Depression Rating Scale (MADRS) Total Score Change from Baseline Model Summary (Intent to Treat Population)
*Table 14.2.2.5	Analysis of Montgomery-Asberg Depression Rating Scale (MADRS) Total Score Change from Baseline at Week 6/EOT (Intent to Treat Population)
Table 14.2.2.6	Montgomery-Asberg Depression Rating Scale (MADRS) Responders Comparison of TS-121 Treatment versus Placebo at Week 6/EOT (Intent to Treat Population)
Table 14.2.3.1	Clinical Global Impression Severity (CGI-S) Score Observed and Change from Baseline by Treatment and Visit (Intent to Treat Population)

# Statistical Analysis Plan

Taisho Pharmaceutical R&D Inc.  
Protocol TS121-US201

Final 2.0  
18 Dec 2018

Statistical Analysis Plan (SAP)

CONFIDENTIAL

Table 14.2.3.2	Summary and Analysis of Clinical Global Impression Improvement (CGI-I) Score Frequency, CGI-I Summary Scores and CGI-I Improver Frequency by Treatment and Visit (Intent to Treat Population)
Table 14.2.3.3	Analysis of Clinical Global Impression Severity (CGI-S) Score Least Squares Treatment Mean Differences by Visit (Intent to Treat Population)
Table 14.2.3.3.1	Multiple Imputation Method for Missing Visits Analysis of Clinical Global Impression Severity (CGI-S) Score Least Squares Treatment Mean Differences by Visit (Intent to Treat Population)
Table 14.2.3.4	Analysis of Clinical Global Impression Severity (CGI-S) Score Change from Baseline Model Summary (Intent to Treat Population)
Table 14.2.3.4.1	Multiple Imputation Method for Missing Visits Analysis of Clinical Global Impression Severity (CGI-S) Score Change from Baseline Model Summary (Intent to Treat Population)
Table 14.2.4.1	Hamilton Anxiety Scale (HAM-A) Total Score Observed and Change from Baseline by Treatment and Visit (Intent to Treat Population)
Table 14.2.4.2	Hamilton Anxiety Scale (HAM-A) Item Scores Response Frequency by Treatment and Visit (Intent to Treat Population)
Table 14.2.4.3	Analysis of Hamilton Anxiety Scale (HAM-A) Least Squares Treatment Mean Differences by Visit (Intent to Treat Population)
Table 14.2.4.3.1	Multiple Imputation Method for Missing Visits Analysis of Hamilton Anxiety Scale (HAM-A) Least Squares Treatment Mean Differences by Visit (Intent to Treat Population)
Table 14.2.4.4	Analysis of Hamilton Anxiety Scale (HAM-A) Change from Baseline Model Summary (Intent to Treat Population)
Table 14.2.4.4.1	Multiple Imputation Method for Missing Visits Analysis of Hamilton Anxiety Scale (HAM-A) Change from Baseline Model Summary (Intent to Treat Population)
Table 14.2.5.1	Symptoms of Depression Questionnaire (SDQ) Total Score Observed and Change from Baseline by Treatment and Visit (Intent to Treat Population)
Table 14.2.5.2	Symptoms of Depression Questionnaire (SDQ) Item Response by Treatment and Visit (Intent to Treat Population)
Table 14.2.5.3	Analysis of Symptoms of Depression Questionnaire (SDQ) Total Score Change from Baseline Least Squares Treatment Mean Differences by Visit (Intent to Treat Population)
Table 14.2.5.3.1	Multiple Imputation Method for Missing Visits Analysis of Symptoms of Depression Questionnaire (SDQ) Total Score Change from Baseline Least Squares Treatment Mean Differences by Visit (Intent to Treat Population)
Table 14.2.5.4	Analysis of Symptoms of Depression Questionnaire (SDQ) Total Score Change from Baseline Model Summary (Intent to Treat Population)

# Statistical Analysis Plan

Taisho Pharmaceutical R&D Inc.  
Protocol TS121-US201

Final 2.0  
18 Dec 2018

Statistical Analysis Plan (SAP)

CONFIDENTIAL

Table 14.2.5.4.1	Multiple Imputation Method for Missing Visits Analysis of Symptoms of Depression Questionnaire (SDQ) Total Score Change from Baseline Model Summary (Intent to Treat Population)
Table 14.2.6.1	Plasma Copeptin and Change from Baseline (Exploratory PD Analysis Population)
Table 14.2.6.2	Analysis of Plasma Copeptin and Change from Baseline at Week 6 (Exploratory PD Analysis Population)
Table 14.2.7.1	Inflammatory Markers (IL-1, IL-6, HS-CRP, and TNF- $\alpha$ ) and Change from Baseline (Intent to Treat Population)
Table 14.2.7.2	Analysis of Inflammatory Markers Change from Baseline at Visit 6 (Intent to Treat Population)
Table 14.2.8.1	Pharmacodynamic Biomarkers, Cortisol in Saliva, Hair and Plasma, Observed and Change from Baseline (Intent to Treat Population)
Table 14.2.9.1	MADRS Total Score Change from Baseline by Patient Characteristic and Treatment (Intent to Treat Population)
SECTION 14.3.1:	Adverse Events
*Table 14.3.1.1	Overall Summary of Adverse Events, Treatment Emergent and with Onset During Placebo Lead-in by Treatment (Safety Analysis Population)
*Table 14.3.1.2	Summary of Adverse Events by System Organ Class, Preferred Term, Severity and Treatment (Safety Analysis Population)
Table 14.3.1.3	Summary of Treatment Emergent Adverse Events by System Organ Class, Preferred Term, Relationship to Study Drug and Treatment (Safety Analysis Population)
SECTION 14.3.2:	Deaths, Serious Adverse Events and Events of Clinical Significance
*Table 14.3.2.1	Serious Adverse Events (Safety Analysis Population)
*Table 14.3.2.2	Events of Clinical Significance (Safety Analysis Population)
SECTION 14.3.4:	Laboratory Abnormal Assessments
Table 14.3.4.1	Abnormal Clinically Significant Clinical Laboratory Values (in Conventional Units) (Safety Analysis Population)
Table 14.3.4.2	Abnormal Clinically Significant Clinical Laboratory Values (in Standard International Units) (Safety Analysis Population)
Table 14.3.4.3	Individual Patients Evaluated for Drug-Induced Serious Hepatotoxicity (Safety Analysis Population)
SECTION 14.3.5:	Laboratory Assessments
Table 14.3.5.1.1	Descriptive Statistics for Clinical Laboratory Results (Conventional Units) (Safety Analysis Population)
Table 14.3.5.1.2	Descriptive Statistics for Clinical Laboratory Results (Standard International Units) (Safety Analysis Population)

# Statistical Analysis Plan

Taisho Pharmaceutical R&D Inc.  
Protocol TS121-US201

Final 2.0  
18 Dec 2018

Statistical Analysis Plan (SAP)

CONFIDENTIAL

Table 14.3.5.2	Summary of Urinalysis Categorical Results (Safety Analysis Population)
Table 14.3.5.3.1	Shift from Baseline to End of Treatment in Biochemistry Laboratory Results (Safety Analysis Population)
Table 14.3.5.3.2	Shift from Baseline to End of Treatment in Hematology Laboratory Results (Safety Analysis Population)
Table 14.3.5.3.3	Shift from Baseline to End of Treatment in Urinalysis Laboratory Results (Safety Analysis Population)
Table 14.3.5.4.1	Number and Percentage of Patients With Clinical Laboratory Outlier Values (Safety Analysis Population) (Safety Analysis Population)
Table 14.3.5.4.2	Individual Patients with Clinical Laboratory Outlier Values (in Conventional Units) (Safety Analysis Population)
Table 14.3.5.5.1	Number and Percentage of Patients With Clinically Noteworthy Laboratory Changes (Safety Analysis Population)
Table 14.3.5.5.2	Individual Patients with Clinically Noteworthy Laboratory Changes (in Conventional Units) (Safety Analysis Population)

## **SECTION 14.3.6: Other Safety Assessments**

Table 14.3.6.1.1	Vital Signs Observed Values (Safety Analysis Population)
Table 14.3.6.1.2	Vital Signs Change from Baseline (Safety Analysis Population)
Table 14.3.6.2.1	Quantitative 12-Lead Electrocardiogram Assessments, Observed Values (Safety Analysis Population)
Table 14.3.6.2.2	Quantitative 12-Lead Electrocardiogram Assessments, Change from Baseline (Safety Analysis Population)
Table 14.3.6.2.3	Categorical Summary of 12-Lead Electrocardiogram QTc (Safety Analysis Population)
Table 14.3.6.2.4	Summary of 12-Lead ECG Interpretations (Safety Analysis Population)
Table 14.3.6.3.1	Body Weight Observed Values (Safety Analysis Population)
Table 14.3.6.3.2	Body Weight Change from Baseline (Safety Analysis Population)
Table 14.3.6.4.1	Ophthalmological Examination Class I Lens Events (Safety Analysis Population)
Table 14.3.6.4.2	Ophthalmological Examination LOCS III Grading and Best Corrected Visual Acuity Score Observed Values (Safety Analysis Population)
Table 14.3.6.4.3	Ophthalmological Examination LOCS III Grading and Best Corrected Visual Acuity Score Change from Baseline (Safety Analysis Population)
Table 14.3.6.5.1	Columbia Suicide Severity Rating Scale (C-SSRS) Shift from Baseline (Safety Analysis Population)
Table 14.3.6.5.2	Columbia Suicide Severity Rating Scale (C-SSRS) Suicidal Ideation Score Observed and Change from Baseline (Safety Analysis Population)

# Statistical Analysis Plan

Taisho Pharmaceutical R&D Inc.  
Protocol TS121-US201

Final 2.0  
18 Dec 2018  
CONFIDENTIAL

Statistical Analysis Plan (SAP)

**Table 3**      **Figures to be Included in Section 14 of the Clinical Study Report**

*Note: Top line figures are indicated \**

---

Figure 14.1.1	Patient Disposition (All Screened Patients)  Refer to shells document.
Figure 14.2.1	Plasma ██████████ Concentrations versus Actual Time Post Dose (Pharmacokinetic Population)  Refer to shells document.  Scatter plot using different symbols for TS-121 10 mg and TS-121 50 mg treatment groups. X-axis is actual time post dose.
*Figure 14.2.2.1	Montgomery-Asberg Depression Rating Scale (MADRS) Total Score Treatment Mean (+/- SE) versus Visit (Intent to Treat Population)  Refer to shells document.  Profile plot using different symbols for TS-121 10 mg, TS-121 50 mg and Placebo treatment groups. X-axis in weeks from Baseline through follow-up. Plot Week 6 or ET at 6 weeks and Follow-up at 10 weeks.
*Figure 14.2.2.2	Montgomery-Asberg Depression Rating Scale (MADRS) Total Score Treatment Mean (+/- SE) Change from Baseline versus Visit (Intent to Treat Population)  Refer to shells document.  Profile plot using different symbols for TS-121 10 mg, TS-121 50 mg and Placebo treatment groups. X-axis in weeks from Baseline through follow-up. Plot Week 6 or ET at 6 weeks and Follow-up at 10 weeks. Reference line at zero change from baseline.
Figure 14.2.3.1	Clinical Global Impression Severity (CGI-S) Score Treatment Mean (+/- SE) versus Visit (Intent to Treat Population)  Profile plot using different symbols for TS-121 10 mg, TS-121 50 mg and Placebo treatment groups. X-axis in weeks from Baseline through follow-up. Plot Week 6 or ET at 6 weeks and Follow-up at 10 weeks.
Figure 14.2.3.2	Clinical Global Impression Severity (CGI-S) Score Treatment Mean (+/- SE) Change from Baseline versus Visit (Intent to Treat Population)  Profile plot using different symbols for TS-121 10 mg, TS-121 50 mg and Placebo treatment groups. X-axis in weeks from Baseline through follow-up. Plot Week 6 or ET at 6 weeks and Follow-up at 10 weeks. Reference line at zero change from baseline.
Figure 14.2.4.1	Hamilton Anxiety Scale (HAM-A) Treatment Mean (+/- SE) versus Visit (Intent to Treat Population)  Profile plot using different symbols for TS-121 10 mg, TS-121 50 mg and Placebo treatment groups. X-axis in weeks from Baseline through follow-up. Plot Week 6 or ET at 6 weeks and Follow-up at 10 weeks.

# Statistical Analysis Plan

Taisho Pharmaceutical R&D Inc.  
Protocol TS121-US201

Final 2.0  
18 Dec 2018

Statistical Analysis Plan (SAP)

CONFIDENTIAL

- Figure 14.2.4.2 Hamilton Anxiety Scale (HAM-A) Treatment Mean (+/- SE) Change from Baseline versus Visit (Intent to Treat Population)
- Profile plot using different symbols for TS-121 10 mg, TS-121 50 mg and Placebo treatment groups. X-axis in weeks from Baseline through follow-up. Plot Week 6 or ET at 6 weeks and Follow-up at 10 weeks. Reference line at zero change from baseline.*
- Figure 14.2.5.1 Symptoms of Depression Questionnaire (SDQ) Total Score Treatment Mean (+/- SE) versus Visit (Intent to Treat Population)
- Profile plot using different symbols for TS-121 10 mg, TS-121 50 mg and Placebo treatment groups. X-axis in weeks from Baseline through follow-up. Plot Week 6 or ET at 6 weeks and Follow-up at 10 weeks.*
- Figure 14.2.5.2 Symptoms of Depression Questionnaire (SDQ) Total Score Treatment Mean (+/- SE) Change from Baseline versus Visit (Intent to Treat Population)
- Profile plot using different symbols for TS-121 10 mg, TS-121 50 mg and Placebo treatment groups. X-axis in weeks from Baseline through follow-up. Plot Week 6 or ET at 6 weeks and Follow-up at 10 weeks. Reference line at zero change from baseline.*
- Figure 14.2.6.1.1 Baseline Montgomery-Asberg Depression Rating Scale (MADRS) Total Score versus Baseline Plasma Copeptin (Intent to Treat Population)
- Refer to shells document.***
- Scatter plot using different symbols for TS-121 10 mg, TS-121 50 mg and Placebo treatment groups. X-axis is baseline plasma copeptin. Plot baseline MADRS total score.*
- Figure 14.2.6.1.2 Montgomery-Asberg Depression Rating Scale (MADRS) Total Score Change from Baseline versus Plasma Copeptin Change from Baseline (Intent to Treat Population)
- Scatter plot using different symbols for TS-121 10 mg, TS-121 50 mg and Placebo treatment groups. X-axis is plasma copeptin change. Plot MADRS total score change.*
- Figure 14.2.6.2.1 Baseline Montgomery-Asberg Depression Rating Scale (MADRS) Total Score versus Baseline Inflammatory Markers (IL-1, IL-6, HS-CRP, and TNF- $\alpha$ ) (Intent to Treat Population)
- Scatter plot, one pager per marker using different symbols for TS-121 10 mg, TS-121 50 mg and Placebo treatment groups. X-axis is baseline Marker. Plot baseline MADRS total score.*
- Figure 14.2.6.2.2 Montgomery-Asberg Depression Rating Scale (MADRS) Total Score Change from Baseline versus Inflammatory Markers (IL-1, IL-6, HS-CRP, and TNF- $\alpha$ ) Change from Baseline (Intent to Treat Population)
- Scatter plot using different symbols for TS-121 10 mg, TS-121 50 mg and Placebo treatment groups. X-axis is inflammatory marker. Plot MADRS total score change.*

# Statistical Analysis Plan

Taisho Pharmaceutical R&D Inc.  
Protocol TS121-US201

Final 2.0  
18 Dec 2018

Statistical Analysis Plan (SAP)

CONFIDENTIAL

- Figure 14.2.6.3 Baseline Montgomery-Asberg Depression Rating Scale (MADRS) Total Score versus Baseline Pharmacodynamic Biomarkers (Intent to Treat Population)
- One page each for salivary cortisol, hair cortisol and 8h urinary cortisol. Scatter plot using different symbols for TS-121 10 mg, TS-121 50 mg and Placebo treatment groups. X-axis is baseline Pharmacodynamic Biomarker (Cortisol level). Plot baseline MADRS total score.*
- Figure 14.2.7.1 Montgomery-Asberg Depression Rating Scale (MADRS) Total Score Change from Baseline versus Baseline Patient Characteristics (Intent to Treat Population)
- Refer to shells document.**
- One page per 'patient characteristic' in Listing 16.2.6.8. Scatter plot using different symbols for TS-121 10 mg, TS-121 50 mg and Placebo treatment groups. X-axis is baseline Patient Characteristic (may be group score). Plot MADRS total score change from baseline. In case of grouped scores in only 2 or 3 groups then present overlay box plots (median with 25th to 75th percentiles) of the MADRS Total score change per group and treatment.*
- Figure 14.3.1.1 Time-matched Post-Baseline Alanine Aminotransferase versus Total Bilirubin (Safety Analysis Population)
- Refer to shells document.**
- One page, two panels. Left is Placebo Group and right is Overall TS-121 Groups. Include scheduled and unscheduled post-baseline assessments. Units are  $\times$ ULN for horizontal and vertical axes and scale is logarithmic.*
- Figure 14.3.1.2 Time-matched Post-Baseline Aspartate Aminotransferase versus Total Bilirubin (Safety Analysis Population)
- As Figure 14.3.1.1.*
- Figure 14.3.2.1 Peak Post-Baseline Alanine Aminotransferase versus Peak Total Bilirubin (Safety Analysis Population)
- As Figure 14.3.1.1, one point per patient and unmatched unscheduled results are included.*
- Figure 14.3.2.2 Peak Post-Baseline Aspartate Aminotransferase versus Peak Total Bilirubin (Safety Analysis Population)
- As Figure 14.3.1.1, one point per patient and unmatched unscheduled results are included.*

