3 SYNOPSIS

[figure not shown]
Protocol Title	A Multicenter, Randomized, Double-blind, Placebo-controlled Study of the Safety and Efficacy of TS-121 as an Adjunctive Treatment for Patients with Major Depressive Disorder with an Inadequate Response to Current Antidepressant Treatment
Protocol Number	TS121-US201
Phase of Development	2a
Number of Study Sites	Approximately 25 US sites
Study Drug	TS-121: An oral, investigational new drug with antagonistic activity of the vasopressin 1b receptor (V _{1b} receptor)
Indication	Major Depressive Disorder (MDD)
Number of Patients	
Approximately 180 randomized male and female MDD patients between 18 and 65 years of age inclusive
 
 • Placebo Group: 60 patients • TS-121 10 mg Group: 60 patients • TS-121 50 mg Group: 60 patients
Objectives	
Primary Objectives
 
 • To evaluate the safety and tolerability of TS-121 compared to placebo in MDD patients • To evaluate the efficacy of two dose levels of TS-121 compared to placebo on MDD symptoms in MDD patients 
Exploratory Objective
 
 • To evaluate the effectiveness of biomarkers in predicting TS-121 response with retrospective stratification of patients via baseline values of HPA axis and inflammatory biomarkers
Safety assessments	
Safety and tolerability will be assessed from the time the patient is administered the investigational product through the final study procedure.
 
Safety variables for assessment will include:
 
 • Adverse events • Physical examination • Columbia Suicide Severity Rating Scale (C-SSRS) • Body weight • Vital signs

	
 • Clinical laboratory tests (hematology, biochemistry and urinalysis) • 12-lead electrocardiogram (ECG) • Ophthalmological examinations
Efficacy assessments	
Primary Endpoint
 
 • Change in MADRS total score from Visit 3 (Baseline) to Visit 6 (EOT) 
Secondary Endpoints
 
 • Changes from Visit 3 (Baseline) to Visit 6 (EOT) for CGI-S, SDQ, and HAM-A total scores • Percentage of CGI-I improvers (“Very much improved” or “Much improved”) • Percentage of MADRS responders ($\geq 50\%$ reduction in total score)

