4.4.3 Known and Potential Risks to Human Subjects

Though the relevance to human subjects is not yet fully understood, nonclinical findings suggested that potential risks include cataract, hepatotoxicity, effects on the gastrointestinal system and effects on the renal system. To date, no apparent trends related to these potential risks were noted in the clinical studies.

Treatment emergent ventricular arrhythmias have been reported following single and multiple dose administrations of TS-121. During the SAD study (TS121-US101), two subjects exposed to 2.5 mg of TS-121 had defined intervals of ventricular arrhythmias while on telemetry. Plasma levels were approximately 50% of C_{max} values (40 to 70 ng/mL). The events were without symptoms, resolved without intervention, and produced no residual effects. The events were considered mild in intensity and possibly related to the study drug. One subject was discontinued from the trial, and one subject completed the trial.

In the MAD study (TS121-US102), one subject showed a single episode of 4 consecutive premature ventricular contractions without symptoms while on telemetry approximately 15 hours

after receiving 50 mg dose of TS-121 on Day 9. The investigator assessed the episode as a clinically significant event and described the event as mild and possibly related to TS-121. The subject completed the trial with no additional events.

In a PET receptor occupancy study (TS121-US103), no abnormal ECG results were reported following single TS-121 doses of up to 50 mg. See Sections 8 and 9 of the Investigator's Brochure for additional information.

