## 2. STUDY OBJECTIVES AND ENDPOINTS

### 2.1 Primary Objectives

- To evaluate the safety and tolerability of TS-121 compared to placebo in MDD patients
- To evaluate the efficacy of two dose levels of TS-121 compared to placebo on MDD symptoms in MDD patients

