## Evaluation of Drug-Induced Serious Hepatotoxicity

The evaluation of drug-induced serious hepatotoxicity (eDISH) will be based on a tabulation by subject number [Table 14.3.4.3] and scatter plot figure. The table will present all scheduled and unscheduled ALT, AST, ALP and TBL of any patient with AST or ALT > 3x ULN or TBL > 2 x ULN. This table will be assessed to identify any incidence of

1. Three-fold or greater elevations above the ULN of ALT or AST and
2. Among patients showing such AT elevations, any patient with elevation of serum TBL to >2xULN and without initial finding of cholestasis (elevated serum ALP).

Side by side scatter plots will be presented of time-matched ALT versus TBL [Figure 14.3.1.1] and time-matched AST versus TBL [Figure 14.3.1.2] grouped to combined TS-121 treatment

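### The four eDISH liver plots pool the 10 mg and 50 mg arms with no dose label, and no specified output counts eDISH cases by arm

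*SAP*

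**What the plan says.** SAP 6.3.16.2, under Evaluation of Drug-Induced Serious Hepatotoxicity, bases the evaluation on a tabulation by subject (Table 14.3.4.3) and on scatter plots of ALT and AST against total bilirubin. The plots are "grouped to combined TS-121 treatment" groups and placebo. SAP Table 3 gives the layout of Figure 14.3.1.1: "Left is Placebo Group and right is Overall TS-121 Groups". Figure 14.3.1.2 takes the same layout. So do the two peak-value plots, 14.3.2.1 and 14.3.2.2: "As Figure 14.3.1.1, one point per patient and unmatched unscheduled results are included". Table 3 specifies no symbol by dose for any of the four.

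Table 14.3.4.3 shows all ALT, AST, ALP and total bilirubin results for any patient with AST or ALT above 3 × ULN, or total bilirubin above 2 × ULN. It is to be assessed for two criteria: (1) ALT or AST at least three times ULN, and (2) among those patients, total bilirubin above 2 × ULN without initial cholestasis.

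Protocol 4.4.3 says that, from nonclinical findings, "potential risks include cataract, hepatotoxicity, effects on the gastrointestinal system and effects on the renal system".

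**The concern.** The trial randomises two doses that differ five-fold, safety and tolerability is a primary objective, and liver injury is a named potential risk. The eDISH figures are the only planned graphs of the joint transaminase and bilirubin pattern. A reader will look there first to see whether raised values cluster at the higher dose. With both doses in one unlabelled panel, the figure cannot answer that, although the arm is known for every randomised patient. The next place to look would be a count of eDISH cases by arm, and the SAP does not specify one.

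**Working it through.** The plan states no rate, power or count for the liver analysis, so there is no figure of its own to reproduce. The check compares the specified outputs and does the arithmetic of the panels.

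**1. How many figures are affected.** The body text and Table 3 agree on pooling, and three figures inherit the layout of the fourth: 4 of 4.

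**2. Comparison within Table 3.** The plots from Figure 14.2.1 (PK) through 14.2.7.1 (MADRS change against patient characteristics) all ask for different symbols for 10 mg and 50 mg. Figure 14.1.1 is a disposition diagram. The four liver plots are therefore the only data plots in Table 3 without dose identification.

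**3. Patients behind each panel.** The Protocol synopsis plans "Placebo Group: 60 patients", "TS-121 10 mg Group: 60 patients" and "TS-121 50 mg Group: 60 patients".
- Placebo panel: 60.
- TS-121 panel: 60 + 60 = 120.
- Ratio: 120 / 60 = 2. At equal risk per patient, the TS-121 panel is expected to hold twice as many cases. In the time-matched plots, unscheduled retests can add further points for one patient.

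**4. What the pooled panel cannot separate.** The documents give no event rate, so case counts are assumptions. Suppose the TS-121 panel holds *k* cases, *j* of them at 50 mg. The panel shows *k* of 120 whatever *j* is. The 50 mg proportion is *j*/60, which can lie anywhere from 0 to *k*/60.

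| Assumed *k* | Panel, *k*/120 | Possible 50 mg proportion |
|---|---|---|
| 2 | 1.7% | 0% to 3.3% |
| 4 | 3.3% | 0% to 6.7% |
| 6 | 5.0% | 0% to 10.0% |

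For *k* = 4, four cases at 50 mg with none at 10 mg (6.7% against 0%) give the same panel as two and two (3.3% each).

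**5. Whether another output supplies what is missing.**
- *Table 14.3.4.3* has the joint values, patient by patient, but only above its entry thresholds. The text does not say that it carries the arm or a count per arm.
- *Table 14.3.5.4.1* counts laboratory outliers one analyte at a time, at the Appendix A cut-offs: ALT or AST above 2.5 × ULN, bilirubin above 1.5 × ULN. Even split by arm, it gives neither criterion 1 nor the joint criterion 2.
- *Table 14.3.5.5.1* counts changes relative to baseline, again by single analyte.
- *Laboratory descriptive statistics and adverse event tables* are by treatment group, but do not pair transaminase with bilirubin.

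A patient with ALT between 2.5 and 3 × ULN and bilirubin between 1.5 and 2 × ULN shows the gap. That patient is plotted without a dose, stays out of Table 14.3.4.3 (unless AST exceeds 3 × ULN), and is counted on two unlinked lines of Table 14.3.5.4.1.

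**The case against.** The strongest reply is that the figures are not where cases are identified. SAP 6.3.16.2 gives that job to Table 14.3.4.3, which shows the joint values for every patient over a threshold. Any such patient can be traced to a dose through the randomisation listing (SAP 6.3.7), and SAP 6.3.1 orders listings by treatment group. SAP 6.3.1 also sets separate 10 mg, 50 mg and placebo columns in summary tables as the general rule. Abnormal laboratory values are listed by randomised treatment, and treatment-emergent adverse events are tabulated by dose. All of this stands. It means that a reader who infers that no dose relation for the liver can be seen anywhere in the report would be wrong.

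A reader might also infer that pooling dilutes a 50 mg signal. The documents do not support that. A scatter plot averages nothing: a point in the high-transaminase, high-bilirubin region is equally visible whichever patients share its panel. Dilution would apply to a pooled proportion or test, and the SAP plans neither. As an illustration only, with assumed rates of 10% at 50 mg and 0% elsewhere, Fisher exact power would fall from 0.56 (50 mg against placebo) to 0.14 (pooled against placebo). That describes a test outside this plan.

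Three further points limit the concern. The objective that names doses is the efficacy one, "To evaluate the efficacy of two dose levels of TS-121 compared to placebo on MDD symptoms in MDD patients"; the safety objective in the same section compares TS-121 with placebo without naming doses. Protocol 4.4.3 reports no apparent clinical trend for the listed risks to date. And Figure 14.3.1.1 refers to a shells document that is not among the public documents, so dose symbols inside the TS-121 panel cannot be excluded. The SAP text, however, does not require them.

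The reply leaves two gaps open: the joint plots have no dose label, including for values too low to enter Table 14.3.4.3, and no output is specified to count either eDISH criterion by arm.

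**Conclusion.** The point holds in a limited form. As SAP 6.3.16.2 and Table 3 are written, the four eDISH figures cannot show whether joint transaminase and bilirubin elevation is related to dose, and no specified output gives the number of patients per arm meeting criterion 1 or criterion 2. The loss is confined to that label and that count.

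It is a minor weakness of presentation. No data are lost, and the primary analysis and sample size are untouched. In the figure alone, an assumed four cases leave the 50 mg proportion open between 0% and 6.7%; for cases over the Table 14.3.4.3 thresholds, tracing patients to their arm by hand would close that range. The conclusion rests on the planned 60 patients per arm and on the unseen shells adding no dose symbols. If they do add them, only the missing per-arm count remains.

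**What to change.** In SAP 6.3.16.2 and Table 3, present the four eDISH figures by randomised arm. Either use three panels (placebo, 10 mg, 50 mg), or keep two panels and apply the 10 mg and 50 mg symbols already used in the other Table 3 plots. In Table 14.3.4.3, add the treatment arm for each patient and a line per arm with the number and percentage meeting criterion 1 and criterion 2, stating the denominator. Bring the shells into line.

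The cost is a shell edit and a few lines of code, with no new data, patients or procedures.
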